18. SAFETY OUTCOMES

All outputs for safety outcomes will be based on the SAF.

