with an amphotericin, persistent visual disturbances with voriconazole, allergic reaction with any compound, or other recognized drug-related AE) AND alternative licensed agents are either predicted to be ineffective or are contraindicated,

- d) **Inability to manage DDIs.** Inability to continue current therapy due to DDIs that cannot be managed AND alternative licensed agents are either predicted to be ineffective or are contraindicated,
- e) **Inability to produce therapeutic drug levels.** Inability to produce or maintain therapeutic blood levels with current therapy AND alternative licensed agents are either predicted to be ineffective or are contraindicated
- f) **An IV-only option (e.g., an amphotericin) has produced a clinical response AND it is standard practice to switch to an oral azole for completion of therapy AND** at least one of the following is true:
 - i) Azole-resistance is known based on susceptibility testing of the infecting isolate,
 - ii) Azole-resistance is predicted by PCR or similar molecular diagnostic tool,
 - iii) Azole-resistance is suspected based on epidemiological or clinical grounds (e.g., development of aspergillosis while on mould-active azole prophylaxis; history of lack of response to a mould-active azole at an early point in the therapeutic course),
 - iv) An azole would be acceptable therapy but it is known or predicted that unmanageable DDIs will occur
- g) **Other MM agreed inclusion.** Patient does not meet any of criteria a) to f), but treatment with F901318 is judged appropriate by the Investigator. Inclusion of patients based on this category must be agreed with the MM and the rationale must be documented.

4.3.1.1 *Inclusion Criteria for Extended Treatment Phase*

1. Patient has completed 84 to 90 days of treatment with F901318 in the main study phase.
2. In the Investigator's opinion the patient has potential to continue to benefit from extended treatment with F901318. The Investigator must discuss ET with the MM, and the MM must approve ET for each patient.
3. No other alternative treatment option is available.
4. Patient is willing to give informed consent for ET.
5. Patient is willing and able to comply with monthly visits to the clinic for assessments.

4.3.2 **Exclusion Criteria for Main Study Phase**

Patients will not be entered in the study for any of the following reasons:

1. Women who are pregnant or breastfeeding.

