8.9.2 Adverse Events

Adverse events will be coded using MedDRA. Number of events and incidence rates will be tabulated by System Organ Class and Preferred Term. An event that occurs at least once on the date of, or subsequent to first administration of study drug will contribute one observation to the numerator of the incidence rate. The denominator of the rate will comprise all patients exposed to the study drug (SAF analysis set). If the intensity or seriousness of the AE changes, the overall severity or seriousness will be the worst severity or seriousness of the multiple occurrences.

TEAEs, SAEs (including deaths), TEAEs leading to death, treatment-emergent AESIs, liver-related TEAEs, TEAEs leading to premature treatment discontinuation and TEAEs leading to premature study withdrawal will be tabulated. In addition, TEAEs by relationship and severity (using CTCAE grading) will be summarised.

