APPENDIX 4: PROTOCOL AMENDMENT HISTORY

The Protocol Amendment Summary of Changes Table for the current amendment is located directly before the Table of Contents (TOC).

Document History

Document	Date	Substantial	Region
Amendment 06	28 February 2020	Yes	Global
Amendment 05	30 October 2019	Yes	Global (not implemented)
Amendment 04	03 May 2019	Yes	Global
Amendment 03	28 November 2018	Yes	Global
Amendment 02	02 May 2018	Yes	Global
Amendment 01-01	07 March 2018	Yes	Local (Belgium)
Amendment 01	24 January 2018	Yes	Global
Original Protocol	19 December 2017	-	-

Amendment 05 30 October 2019

Amendment 05 was not implemented. Changes introduced to Amendment 05 which are relevant to Amendment 06 are included in the Summary of Changes for Amendment 06.

Amendment 04 03 May 2019

This amendment is considered to be substantial based on the criteria set forth in Article 10(a) of Directive 2001/20/EC of the European Parliament and the Council of the European Union.

Overall Rationale for Amendment 04

An extended treatment phase has been added to the study to allow continued treatment with F901318 for those patients who have benefitted from treatment with F901318 during the 90 day study treatment period, have no suitable alternative treatment options and would continue to benefit from extended treatment. In prior versions of this protocol, extended treatment has been provided via a Named Patient mechanism in each territory. As is standard with Named Patient mechanisms, the ability of the Sponsor to closely follow and support patients is limited and the data from patients utilizing this mechanism is not incorporated into study reports. As it has become clear that extended treatment is being found beneficial in approximately 25% of enrolled patients, Amendment 04 provides an explicit mechanism for this process that will allow the data from these patients to ultimately be provided as an addendum to the primary report for this study.

Extended treatment is to be requested by the Investigator and must be approved by the Medical Monitor. Patients will attend visits every 4 weeks during extended treatment to assess the safety

of continued treatment and to confirm by the evaluation of efficacy that continued treatment is justified. Assessment of the safety and efficacy of F901318 during extended treatment has been added as an exploratory objective. Detail has been presented of the assessments and procedures to be completed during extended treatment.

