Patient-reported outcomes have been added as an endpoint, to be collected by completion of the EQ-5D-5L questionnaire. This will provide additional insight into the benefits of treatment with F901318.

Further detail has been added for efficacy and safety assessments to clarify the processes for these assessments and to improve the consistency of reporting.

Description of Changes in Amendment 04:

Section Number and Name	Description of Change	Brief Rationale
Title page	
Sponsor address in the UK has been deleted.
 
The Project Manager details have been updated.
	
The Sponsor address is now in Austria.
 
The [REDACTED] Project Manager has changed.

Synopsis; Section 4.1	
The numbers of centres has been increased from 40 to 50.
	
The number of centres has been increased to facilitate enrolment of patients.

Synopsis; Section 3.2; Section 4.1; Section 6.3.4; Section 8.8.3	
Patient-reported outcomes have been added, to be collected by completion of the EQ-5D-5L questionnaire.
	
The EQ-5D-5L is a validated questionnaire to evaluate the effect of treatment on the patients quality of life, and will provide additional insight into the benefit profile of F901318.

Synopsis; Section 3.4	
An Extended Treatment Exploratory Objective has been added: To describe the efficacy and safety of prolonged treatment with F901318 for infections due to resistant fungi in patients lacking suitable alternative treatment options.
	
It is estimated that approximately 25% of patients who respond to treatment with F901318 may require treatment beyond the maximum of 90 days of treatment included in the main phase of this protocol. Safety and efficacy data collected from the end of the main study phase onwards will be evaluated as an exploratory objective.

Synopsis; Protocol body text throughout	
Reference to treatment with F901318 beyond Day 90 'via an extended dosing mechanism that is outside the scope of this protocol' has been replaced by a description of 'an extended treatment phase'.
	
This change provides a more structured approach to management of patients who have responded to treatment with F901318, and who have a clinical need and are likely to continue to benefit from extended treatment beyond Day 90 of the main study.

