5.6. SAFETY ANALYSIS SET [SAF]

The safety analysis set (SAF) will contain all patients who receive at least one dose of study medication (or part thereof).

If there is any doubt whether a patient was treated or not, they will be assumed treated for the purposes of analysis.

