18.1. ADVERSE EVENTS

Adverse Events will be coded using the most recent version of MedDRA.

- TEAEs will be presented by phase; TEAEs occurring in the main phase, TEAE's occurring in the extended phase, and TEAEs occurring in main or extended phase.

Document: \\weedc-vnasc01\BIOSdata\F2G\F901318 [REDACTED]
Author: [REDACTED] Version Number: 3.0
Version Date: 06Apr2023
Template No.: CS_TP_BS016 Revision 6 Reference: CS_WI_BS005
Effective Date: 02Dec2019

- TEAEs occurring in the main phase are defined as any AE which started or worsened on or after the first dose of main phase study treatment up to and including the post-treatment follow-up for the main phase.
- TEAEs occurring in the extended phase are defined as any AE which started or worsened on or after the first dose of extended phase study treatment up to and including the post-treatment follow-up for the extended phase. Note that if an AE occurred during the main phase, but worsened during the extended phase, the event qualifies as occurring in both main and extended phase. TEAEs occurring in main or extended phase are defined as any AE which started or worsened on or after the first dose of main phase study treatment up to and including the post-treatment follow-up for the extended phase.

See [appendix 2](#) for handling of partial dates for AEs. In the case where it is not possible to define an AE as treatment-emergent or not, the AE will be classified by the worst case; i.e. treatment-emergent.

A table listing the TEAEs with overall frequency >3% by preferred term in decreasing order of number of subjects with at least one TEAE in the preferred term will be presented.

Listings will include TEAEs and Non-TEAEs.

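### Extended-phase adverse event percentages are based on the whole safety set, so they are understated by a factor of one over the share of patients entering extended treatment

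*SAP*

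**What the plan says.** Four statements bear on the point.

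- **Population for safety outputs.** SAP 18: "All outputs for safety outcomes will be based on the SAF". No exception is made for extended-phase outputs.
- **What the SAF is.** SAP 5.6: "The safety analysis set (SAF) will contain all patients who receive at least one dose of study medication (or part thereof". Patients who were treated only in the main phase are therefore included.
- **Adverse event denominator.** Protocol 8.9.2: "The denominator of the rate will comprise all patients exposed to the study drug (SAF analysis set".
- **Presentation by phase.** SAP 18.1: "TEAEs will be presented by phase; TEAEs occurring in the main phase, TEAE's occurring in the extended phase", followed by a main-or-extended presentation. An extended-phase TEAE is "any AE which started or worsened on or after the first dose of extended phase study treatment", up to the end of the extended-phase follow-up.

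Entry to ET is restricted. Protocol 4.3.1.1 requires: "Patient has completed 84 to 90 days of treatment with F901318 in the main study phase". SAP 5 defines seven analysis sets, and none is specific to ET.

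**The concern.** A patient who died, stopped early, or finished in the main phase without going on to ET cannot have an extended-phase TEAE. That patient still counts in the denominator if the SAF is used. The resulting percentage mixes two things: how often events occurred among those on extended dosing, and how few patients received it.

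The documents give 90 days as the longest nonclinical toxicology exposure (protocol 4.1 and 5.1), and liver monitoring continues into ET (protocol Appendix 3). Extended-phase incidence is one of the summaries a reader will use to judge exposure beyond that limit. Set beside a main-phase column on the same SAF base, the extended phase would look better tolerated partly because fewer patients were exposed.

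The plan restricts the population elsewhere. Laboratory, ECG and vital-sign abnormalities use patients at risk (SAP 18.2.3, 18.3.2, 18.4.2). Efficacy and mortality at the 4-week follow-up consider only patients who did not go on to ET (SAP 16.1.5). Extended-phase adverse events have no matching rule.

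**Working it through.** The plan states no figure for this quantity, so there is nothing to reproduce.

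**Formula.** Let x be the number of patients with an extended-phase TEAE, N_SAF the number in the SAF, N_ET the number with at least one ET dose, and s = N_ET / N_SAF.

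- Percentage under the SAF rule: x / N_SAF
- Percentage among patients who can have the event: x / N_ET
- Understatement factor: (x / N_ET) / (x / N_SAF) = N_SAF / N_ET = 1/s

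The factor does not depend on x.

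**Inputs.** Planned enrolment is about 200 (SAP 3.1), used here as an approximation to N_SAF. The initial CSR covers 100 patients (SAP 4.3). The ET share appears only in the Amendment 04 material in protocol Appendix 4, on two bases. The overall rationale says "extended treatment is being found beneficial in approximately 25% of enrolled patients". The change table says "approximately 25% of patients who respond to treatment with F901318 may require treatment beyond the maximum of 90 days". They serve here only as inputs; the difference between them is not raised as an error in the current plan.

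**25% of treated patients.** N_ET = 0.25 × 200 = 50, and the factor is 200/50 = 4.0. For the initial CSR, 100/25 = 4.0 as well. As an illustration, take 10 patients with an event (exact Clopper-Pearson intervals):

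- SAF base: 10/200 = 5.0% (95% CI 2.4 to 9.0%)
- ET entrants: 10/50 = 20.0% (95% CI 10.0 to 33.7%)

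**Other shares of treated patients (assumed).**

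| Share entering ET | N_ET of 200 | Factor 1/s |
|---|---|---|
| 15% | 30 | 6.7 |
| 20% | 40 | 5.0 |
| 25% | 50 | 4.0 |
| 30% | 60 | 3.3 |
| 40% | 80 | 2.5 |
| 50% | 100 | 2.0 |
| 60% | 120 | 1.7 |

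**25% of responders only.** The share of treated patients is then 0.25 × response rate. For an assumed response rate of 30% to 75%, the share is 0.25 × 0.30 = 7.5% to 0.25 × 0.75 = 18.75%. The factor runs from 1/0.075 = 13.3 down to 1/0.1875 = 5.3.

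**The case against.** **The denominator is inferred.** SAP 18 says outputs are based on the SAF; it does not spell out the percentage base for extended-phase adverse events. Laboratory, ECG and vital-sign incidences are also safety outputs, yet they use at-risk bases. SAP Appendix 1 permits a denominator other than the population count if it is shown, and the table templates (SAP 8) are not in the available text. This stands as a caution about what the shells may contain. It does not remove the point: the permission assigns no other base to these tables, and the stated rules lead to the SAF. If the shells already use ET entrants, the SAP text contradicts them and still needs correcting.

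**Protocol 8.9.2 was not written for ET tables.** Protocol 8.2.4 and 8.9 send ET events to a report addendum. This is fair, and it makes 8.9.2 the weaker support. SAP 18 carries the point alone, because it covers every safety output and SAP 18.1 creates the extended-phase presentation.

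**A reader can rescale, and other safeguards exist.** This stands. The number entering ET is summarised (SAP 9.1), ET exposure is tabulated (SAP 14), and ET patients have narratives (SAP 3.1, 4.3). The IDSMB and the Hepatic Advisory Committee review ET data (protocol 6.4.4). These limit the harm, but a safety percentage should not need rescaling by the reader.

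**The frequency-cut table.** A reader might infer that the table of TEAEs above 3% is also cut on the wrong base for the extended phase. The documents do not support this. SAP 18.1 specifies that table for overall frequency and does not say it is produced for the extended phase alone.

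**Conclusion.** The point holds as a should-fix. Followed as written, the plan understates extended-phase incidence percentages by 1/(share of SAF patients entering ET).

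A reader might infer a fixed 4-fold understatement. The documents do not establish that size. It requires about 25% of treated patients to enter ET, which is an approximate 2019 figure from an amendment rationale, and the same log also gives 25% on the smaller base of responders. No current protocol or SAP section states a share. The direction is certain whenever some SAF patients do not enter ET; the size will be known only from the actual entry count.

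A reader might also treat this as an error that compromises the study's conclusions. It does not. Patient counts are unaffected, the main-phase and main-or-extended columns correctly use the SAF, the analyses are generally descriptive (SAP 6), ET is an exploratory objective (protocol 3.4), and no primary result or decision rule uses the affected percentages.

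**What to change.** 1. Add to SAP 5 an Extended Treatment Safety Set: SAF patients with at least one extended-phase dose.
2. Amend SAP 18 so that extended-phase adverse event summaries use this set as both N and denominator. This covers TEAEs, and serious events, AESIs, discontinuations and deaths wherever these are shown by phase.
3. Keep the SAF for the main-phase and main-or-extended columns.
4. Optionally add exposure-adjusted rates, because ET duration varies widely (the SAP 14 categories run past 365 days) and crude incidence among entrants is still not directly comparable with the main phase. Time at risk should then start at the first ET dose. The extended-phase duration in SAP 14.1 runs from the first main-phase dose and would not serve.

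The cost is a short SAP amendment, one analysis flag and updated column headers. No new data are needed and main-phase results do not change. Extended-phase percentages will be higher than under the current rule, with wider intervals where intervals are shown.

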18.1. ADVERSE EVENTS

Adverse Events will be coded using the most recent version of MedDRA.

- TEAEs will be presented by phase; TEAEs occurring in the main phase, TEAE's occurring in the extended phase, and TEAEs occurring in main or extended phase.

Document: \\weedc-vnasc01\BIOSdata\F2G\F901318 [REDACTED]
Author: [REDACTED] Version Number: 3.0
Version Date: 06Apr2023
Template No.: CS_TP_BS016 Revision 6 Reference: CS_WI_BS005
Effective Date: 02Dec2019

- TEAEs occurring in the main phase are defined as any AE which started or worsened on or after the first dose of main phase study treatment up to and including the post-treatment follow-up for the main phase.
- TEAEs occurring in the extended phase are defined as any AE which started or worsened on or after the first dose of extended phase study treatment up to and including the post-treatment follow-up for the extended phase. Note that if an AE occurred during the main phase, but worsened during the extended phase, the event qualifies as occurring in both main and extended phase. TEAEs occurring in main or extended phase are defined as any AE which started or worsened on or after the first dose of main phase study treatment up to and including the post-treatment follow-up for the extended phase.

See [appendix 2](#) for handling of partial dates for AEs. In the case where it is not possible to define an AE as treatment-emergent or not, the AE will be classified by the worst case; i.e. treatment-emergent.

A table listing the TEAEs with overall frequency >3% by preferred term in decreasing order of number of subjects with at least one TEAE in the preferred term will be presented.

Listings will include TEAEs and Non-TEAEs.

18.1.1. ALL TEAEs

Incidence of TEAEs will be presented by SOC and PT and broken down further by maximum severity and relationship to study treatment.

18.1.1.1. Severity

Severity is classed as mild (grade 1)/ moderate (grade 2)/ severe (grades 3, 4 and 5) (increasing severity using Common Terminology Criteria for Adverse Events [CTCAE] grading). TEAEs starting after the first dose of study treatment with a missing severity will be classified as severe. If a patient reports a TEAE more than once within that SOC/ PT, the AE with the worstcase severity will be used in the corresponding severity summaries.

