
- Overall incidence of:
 - AEs.
 - Serious AEs (SAE) (including deaths).
 - AEs leading to premature treatment discontinuation.
 - AEs leading to premature study withdrawal.
 - AEs by relationship.
 - AEs by severity (common terminology criteria for adverse event [CTCAE] grade).
 - AEs of Special Interest (AESI).
- Changes from baseline during the treatment period and at FU in:
 - Vital signs (including weight and body mass index [BMI]).
 - Clinical laboratory assessments and incidence of pre-defined abnormalities.
 - Electrocardiogram (ECG) results and incidence of pre-defined abnormalities.
 - Physical examination findings.
- [REDACTED].
- Changes in concurrent medication dose and/or frequency resulting from potential DDIs.
- Overall exposure, individual dose modification, dose intensity.

Pharmacokinetics:

- PK data (C_{min} ; C_{max} , T_{max} , $AUC_{0-\tau}$, CL/F and Vz/F).
- Effect of concomitant medication on PK profiles.

Statistical Methods:

Sample Size Determination:

This is an open-label study, with no randomization or stratification. There is no upper limit to the enrolment of patients with culture-proven infections. [REDACTED]

[REDACTED]. Total enrolment into the study is anticipated to be approximately 200 patients. This will enable patients who have no suitable treatment options for their invasive fungal disease and are ineligible for the Phase III trial to enrol into Study 32 and receive treatment with F901318.

F901318 has been granted Breakthrough Therapy Designation by the FDA based on preliminary clinical evidence that demonstrates F901318 may provide substantial improvement over available therapy. As this designation is intended to expedite the development and review of important products, an initial analysis of data will be performed when 100 patients have completed treatment, to enable the Sponsor to formally consider the possibility that initial approval might be achieved based on the data for the population of patients with limited or no treatment options for life-threatening fungal infections.

Analysis Sets:

The analysis sets to be used in this study are:

- All Patients Enrolled analysis set: all patients who provide written informed consent.
- Safety analysis set (SAF): consists of all patients who receive at least one dose of study drug (or part thereof). The SAF will be used for the analysis of all safety data.

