[REDACTED]	[REDACTED]	[REDACTED]	[REDACTED]
[REDACTED]	[REDACTED]	[REDACTED]	[REDACTED]
[REDACTED]	[REDACTED]	[REDACTED]	[REDACTED]
[REDACTED]	[REDACTED]	[REDACTED]	[REDACTED]
[REDACTED]	[REDACTED]	[REDACTED]	[REDACTED]
[REDACTED]	[REDACTED]	[REDACTED]	[REDACTED]
[REDACTED]	[REDACTED]	[REDACTED]	[REDACTED]
[REDACTED]	[REDACTED]	[REDACTED]	[REDACTED]
[REDACTED]	[REDACTED]	[REDACTED]	[REDACTED]

Severity

The severity of the AE will be characterized in accordance with CTCAE criteria (V5.0). If the AE is not defined by CTCAE criteria, the severity of the AE will be characterized as “mild, moderate or severe” according to the following definitions:

- Mild events are usually transient and do not interfere with the patient’s daily activities
- Moderate events introduce a low level of inconvenience or concern to the patient and may interfere with daily activities
- Severe events interrupt the patient’s usual daily activity.

Relationship

The causal relationship between the study drug and the AE has to be characterized as unrelated, unlikely, possible, probable or unknown (unable to judge).

Events can be classified as “unrelated” if there is not a reasonable possibility that the study drug caused the AE.

An “unlikely” relationship suggests that only a remote connection exists between the study drug and the reported AE. Other conditions, including chronic illness, progression or expression of the disease state or reaction to concomitant medication, appear to explain the reported AE.

A “possible” relationship suggests that the association of the AE with the study drug is uncertain; however, the AE is not reasonably supported by other conditions.

A “probable” relationship suggests that a reasonable temporal sequence of the AE with drug administration exists and, in the Investigator’s clinical judgment, it is likely that a causal relationship exists between the drug administration and the AE, and other conditions (concurrent illness, progression or expression of disease state or concomitant medication reactions) do not appear to explain the AE.

All efforts should be made to classify the AE according to the above categories. The category “unknown” (unable to judge) may be used only if the causality is not assessable, e.g., because of insufficient evidence, conflicting evidence, conflicting data, or poor documentation.

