8.2.4 Safety Endpoints

Descriptive statistics will be used to present the safety outcomes including:

- Changes in concurrent medication dose and/or frequency resulting from potential DDIs
- Hospitalisations
- Overall exposure, individual dose modification, dose intensity.
- Incidence of treatment-emergent and other (including but not limited to):
 - AEs
 - SAEs (including deaths)
 - AEs leading to death
 - Liver-related AEs
 - AEs leading to premature treatment discontinuation
 - AEs leading to premature study withdrawal
 - AEs by relationship

- AEs by severity (CTCAE grade)
- AESIs
- Change from baseline in clinical laboratory test results and incidence of pre-defined treatment-emergent abnormalities (CTCAE)
- Liver-related toxicity: Incidence and time-to-event analyses of elevations in ALT, AST, bilirubin, as described in detail in Section 6.4.2.3.
- Change from baseline in ECG results and incidence of pre-defined treatment-emergent abnormalities (CTCAE)
- Change from baseline in vital signs (including weight and BMI) and incidence of pre-defined treatment-emergent abnormalities (CTCAE)
- [REDACTED]
- Physical examination: Any abnormal clinically significant findings, as judged by the Investigator, will be listed in a by-patient data listing only.

A treatment-emergent AE (TEAE) is defined as any AE starting or worsening on or after the first dose of study drug up to and including last dose of study drug or during the post-treatment FU. Treatment-emergent AEs which occur in the main study phase or FU will be presented in the study report; TEAEs which occur in the ET phase or post-ET FU will be presented in the report addendum.

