18.1.7. CTC GRADING FOR ADVERSE EVENTS

AEs will be graded using the Common Toxicity grading (CTC) system as defined in:

Common Terminology Criteria for Adverse Events (CTCAE) v5.0.

CTC grades are assigned by the study centres and will not be programmatically verified by IQVIA Biostatistics.

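### SAP 18.1.1.1 puts CTCAE grades 3, 4, 5 and missing severity in one class, so the described AE summary tables cannot tell grade 4 TEAEs from grade 3

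*SAP*

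**What the plan says.** **Protocol.** The synopsis lists among the safety criteria "AEs by severity (common terminology criteria for adverse event [CTCAE] grade". Section 8.2.4 repeats the endpoint as "AEs by severity (CTCAE grade", and section 8.9.2 plans the matching analysis: "TEAEs by relationship and severity (using CTCAE grading) will be summarised". On how severity is scored, section 6.4.1 says "The severity of the AE will be characterized in accordance with CTCAE criteria (V5.0". A mild, moderate or severe rating is allowed there only for events that CTCAE does not define.

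**SAP.** Section 18.1.1 plans TEAE incidence by system organ class and preferred term, "broken down further by maximum severity and relationship to study treatment". Section 18.1.1.1 defines the levels: "Severity is classed as mild (grade 1)/ moderate (grade 2)/ severe (grades 3, 4 and 5". It adds that "TEAEs starting after the first dose of study treatment with a missing severity will be classified as severe". Section 18.1.7 confirms that individual grades exist ("CTC grades are assigned by the study centres") but describes no AE table by grade. The legible part of section 3.3, which lists changes from the protocol, does not mention the pooling.

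**The concern.** The protocol names an endpoint on the CTCAE grade scale, and the SAP delivers it on a coarser one. In effect, the scale that the protocol keeps for events outside CTCAE is applied to every TEAE. The grades that are merged are the ones that matter most to a reader of the safety section.

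The protocol itself treats grade 4 as distinct. Its Table 6 has separate columns for grade 3 (severe) and grade 4 (potentially life-threatening).

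The trial has no control arm, so the safety account rests on describing what happened. Protocol 8.1 says that the analysis of the first 100 patients is meant to let the sponsor consider whether initial approval is achievable. A count of patients with a grade 4 TEAE, and of those with a related one, is a basic part of that account.

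**Working it through.** No figure in the plan bears on this point, so there is nothing to recompute. The check is whether any AE output described in the SAP separates grade 4 from grade 3.

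**Step 1: what the severe row holds.** Under SAP 18.1.1.1 it holds grade 3, grade 4, grade 5 and missing severity. An event that CTCAE does not define and the investigator rates severe (protocol 6.4.1) presumably falls there too. Three of the five CTCAE grades share one row with at least one non-grade category.

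**Step 2: the other described outputs.**

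| Output | Does it separate grade 4 from grade 3? |
|---|---|
| Serious TEAEs, also by relationship (SAP 18.1.4) | No. Under protocol 6.4.1, seriousness also covers hospitalisation, disability and medically significant events. |
| Fatal TEAEs by SOC and PT (SAP 18.1.5) | No, but it largely recovers grade 5. A relationship breakdown of fatal events is described only for AESIs (SAP 18.1.6). |
| AESI summaries (SAP 18.1.6, legible part) | No. They are by category, SOC, PT, relationship and action taken. |
| TEAEs leading to discontinuation, withdrawal or dose adjustment (SAP 18.1.2, 18.1.3, 18.1.8) | No. |
| Laboratory CTC tables (SAP 18.2 and 18.2.3) | Yes, for laboratory values with numeric cut-offs. ALT and AST, for example, are split at 20 times the limit or baseline. They carry no causality assessment. For anaemia, hypoalbuminaemia and hyperglycaemia, grade 4 is defined by clinical consequences and not by a cut-off. |
| AE listings (SAP 18.1) | They cover TEAEs and non-TEAEs, but their columns are not specified in the text. They are not a summary. |

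**Step 3: what a reader could deduce.** For a given preferred term, let S be the patients in the severe row and F the patients in the fatal-TEAE table. Assume that every fatal event is graded 5, so that the F patients are among the S. The remaining S − F patients have a maximum of grade 4 or grade 3, a missing severity, or a severe rating outside CTCAE. The grade 4 count is then bounded only by

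0 ≤ grade 4 count ≤ S − F.

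The serious-TEAE table does not reliably narrow this range, because a grade 3 event can be serious and seriousness is not defined by grade.

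**The case against.** Four counter-arguments deserve weight.

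- **Little is lost from the trial.** This is correct. Individual grades are collected, TEAEs are listed, and fatal TEAEs are counted by preferred term. A reader might infer that life-threatening and fatal events cannot be recovered at all, or that the report could not count fatal events. The documents do not support either inference.
- **Hepatic grade 4 is visible elsewhere.** This is also correct. The protocol's grade 4 reporting trigger for transaminases is a laboratory threshold (ALT or AST above 20 times ULN). SAP 18.2.3 keeps grades 3 and 4 apart for ALT and AST, and protocol 8.9.3 plans incidence tables at 3, 5, 10 and 20 times ULN. A reader might infer that severe liver toxicity would be hidden. It would not be, and the point should not rest on that example.
- **Three classes built from CTCAE grades still use CTCAE grading, and a three-level scale can hold every event.** This fits the wording of protocol 8.9.2, and neither 8.2.4 nor 8.9.2 asks in terms for a five-level table. It fits the endpoint wording in the synopsis and 8.2.4 less well, since both name the grade itself. Events outside CTCAE need a row of their own, not a coarser scale for all the others.
- **The output templates may show more.** SAP section 8 refers to templates that are not among the documents, and parts of SAP 3.3 and 18.1.6 are redacted. A by-grade display or a declared change cannot be excluded. This limits the conclusion to what the legible SAP describes. If the templates do show grades, the text of 18.1.1.1 still needs to agree with them.

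**Conclusion.** The point holds for the AE summaries. As described in the legible SAP, they do not deliver the protocol's endpoint of adverse events by CTCAE grade. Grade 4 TEAEs cannot be told from grade 3 or missing-grade TEAEs overall, by preferred term or by relationship, and the grade 4 count is known only to lie between 0 and S − F. The missing-severity rule makes this worse, because it adds ungraded events to the class whose composition is already unclear.

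The consequence is limited. No efficacy result changes, no estimate is biased, and the grades needed to repair the tables are already collected. The gap matters most for events without a numerically graded laboratory counterpart.

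The conclusion assumes that no by-grade AE table sits in the unseen templates or redacted text. The S − F bound also assumes that fatal events are graded 5.

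**What to change.** In SAP 18.1.1.1:

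- Tabulate TEAEs, and separately related TEAEs, by maximum CTCAE grade 1, 2, 3, 4 and 5, overall and by SOC and PT, with a subtotal for grade 3 or higher.
- Show missing grade as its own row instead of counting it as severe, and state how a missing grade ranks when the same patient also has a graded event under that term.
- Show events rated severe that CTCAE does not define as a separate row.
- Keep the three-level table, with its worst-case rule for missing severity, as a secondary display if wanted.

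If the sponsor prefers to keep the pooling as the main display, record it in SAP 3.3 as a change from the protocol, with the reason.

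The cost is a few lines of SAP text and a wider table. No new data are needed.
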